11.14.5 Definition of Serious Adverse Event

A SAE is defined as any untoward medical occurrence that, at any dose:

- Results in death;
- Is life-threatening;
- Requires inpatient hospitalization or prolongation of existing hospitalization;
- Results in persistent or significant disability/incapacity;
- Is a congenital anomaly/birth defect, or;
- Is otherwise considered to be an important medical event. The event may not be immediately life-threatening or result in death or hospitalization but may jeopardize the patient or may require intervention to prevent one of the other outcomes listed in the definition above. Medical and scientific judgement should be exercised in deciding whether an event should be considered as an Important Medical Event. Examples of such medical events include:
 - o Allergic bronchospasm requiring intensive treatment in an emergency room or at home;
 - o Blood dyscrasias or convulsions that do not result in hospitalization;
 - o Development of drug dependency or drug abuse.

Definitions of terms:

Life-threatening: An AE that is considered to be life-threatening when a subject is at immediate risk of death from the event as it occurred; i.e., it does not include a reaction that if it had occurred in a more serious form might have caused death.

Hospitalization: AEs requiring hospitalization should be considered SAEs. In general, hospitalization signifies that the subject has been detained (usually involving at least an overnight stay) at the hospital or emergency ward for observation and/or treatment that would not have been appropriate in the physician's office or outpatient setting. When in doubt as to whether 'hospitalization' occurred or was necessary, the AE should be considered serious.

Hospitalization for elective surgery or routine clinical procedures that are not the result of AE (e.g., elective surgery for a pre-existing condition that has not worsened) need not be considered AEs or SAEs. If anything untoward is reported during the procedure, that occurrence must be reported as an AE, either 'serious' or 'non-serious' according to the usual criteria.

Disability/incapacity: An AE is incapacitating or disabling if the experience results in a substantial and/or permanent disruption of the subject's ability to carry out normal life functions.

11.14.6 Reporting of Serious Adverse Events

Any SAE will be reported to the Syneos Pharmacovigilance group via e-mail or fax within 24 hours of knowledge by the Investigator, and then in writing within 24 hours of awareness of the SAE. The notification must be directed to:

safety [contact]

[contact]

The Syneos Pharmacovigilance group will provide the report to the Sponsor. The notification must be directed to:

[contact]

11.14.7 Suspected, Unexpected, Serious Adverse Drug Reactions

11.14.7.1 Fatal or Life-threatening Serious, Unexpected Adverse Drug Reactions

The Sponsor is responsible for notifying regulatory agencies of fatal or life-threatening serious, suspected, unexpected adverse drug reactions (by telephone, facsimile transmission or in writing) as soon as possible, but no later than 7 calendar days after becoming aware of the information. Additionally, within 8 days after having informed the agency(ies), a complete report must be submitted, including an assessment of the importance and implication of any findings. Syneos Health will handle notifications to the Canadian regulatory agency on behalf of the Sponsor.

It is the responsibility of the clinical site to report as soon as possible, but no later than 7 calendar days after first knowledge by the Investigator, fatal or life-threatening serious, suspected, unexpected adverse drug reactions to the IRB responsible for the study.

11.14.7.2 Other Suspected, Unexpected, Serious Adverse Drug Reactions

The Sponsor is responsible for notifying regulatory agencies of all other suspected, unexpected, serious adverse drug reactions that are neither fatal nor life-threatening as soon as possible, but no later than 15 calendar days after becoming aware of the information. Syneos Health will handle notifications to the Canadian regulatory agency on behalf of the Sponsor.

It is the responsibility of the clinical site to report to the IRB responsible for the study all other suspected, unexpected, serious adverse drug reactions that are neither fatal nor life-threatening, as soon as possible, but no later than 15 calendar days after first knowledge by the Investigator.

11.15 Pregnancy

In the event the female partner of a dosed male subject becomes pregnant during or shortly after participation in the study, this pregnancy will be reported to the Sponsor within 24 hours of first knowledge of the event. Follow-up information regarding the course and outcome of the pregnancy will be documented (after obtaining the consent of the female partner) as per site's SOP. If the outcome of the pregnancy meets the criteria for classification as an SAE, reporting of the event to the IRB and regulatory agency(ies) will be performed as per site's SOP.

11.16 Reportable Disease

In the case a subject has or manifests any clinical signs characteristic of a reportable disease or condition (e.g., HIV, tuberculosis, SARS, SARS-CoV-2), it is the responsibility of the Medical Director to notify the Public Health authorities within 48 hours after becoming aware of the information.

11.17 Premature Termination of the Study

The study may be prematurely terminated by the Investigator following consultation with the Sponsor, by the Sponsor or by the regulatory authorities. Following a decision to discontinue the trial, the Investigator will promptly inform the active study subjects and the IRB responsible for this trial, stating the reasons for discontinuation of the study and, furthermore, advise them in writing of any potential risks to the health of study subjects or other persons. It is the Sponsor's responsibility to report the premature termination of the study to the regulatory authority(ies), when required by the applicable regulatory requirement(s). The Canadian regulatory agency must be informed of premature termination within 15 days, provided with the reasons for the trial discontinuation and of any potential risks to the health of study subjects or other persons. Syneos Health may notify the Canadian regulatory agency on behalf of the Sponsor upon his request.

12. Analytical Methodology

When applicable, samples will be transported to the bioanalytical facility in at least two separate shipments, with each set of aliquots in separate shipments. Once the bioanalytical laboratory confirms receipt of the first shipment, the second set of aliquots may be sent. The samples should be packed on sufficient dry ice to keep them frozen for at least 72 hours.

The Bioanalytical Division of Syneos Health will analyze NS101 in serum and in CSF, FAM19A5 in CSF and in plasma, and ADAs/NAbs samples using validated methods. NAbs will be analyzed only for subjects with ADA positive results.

For PK, the primary sample will be sent to Syneos Health for bioanalysis. Back up sample shipment will be determined whether they will be shipped along with primary sample of next cohort. Detailed frequency of sample shipment will be described in Laboratory Manual for PK, ADAs, and NAbs.

Biomarker sampling for PD analysis (FAM19A5) will be done and analytical method will be technically transferred by Sponsor to Syneos Health's bioanalytical laboratory, so that sample storage condition and period of storage will need to be documented at that moment. Biobanking of samples for PD analysis (FAM19A5 ELISA) will be done after their collection. Samples will be stored under -70°C until analysis and will be analyzed only after completion of each cohort. Details on sample processing and storage will be included in a Laboratory Manual generated by Syneos Health's bioanalytical laboratory. Although there will be a time gap between collection and time of analysis, these biobanked samples will be analyzed only for PD biomarkers, as described above. No genetic analysis will be done.

The bioanalytical work in support of the study will be conducted in compliance with the GCP, using the SOPs in place in the Bioanalytical Division of Syneos Health. These SOPs are in accordance with applicable regulations in the industry: Guidelines on Bioanalytical Method Validation, Good Laboratory Practice (GLP), and Guideline for GCP ICH E6 (R2).

13. Safety/Tolerability, Pharmacokinetic and Statistical Analyses

PK analysis will be performed using Phoenix $^{\text{@}}$ WinNonlin $^{\text{@}}$. Inferential statistical analyses will be performed using SAS $^{\text{@}}$ according to FDA guidelines.

13.1 Analysis Populations

13.1.1 Safety Population

The safety population is defined as all subjects who received any amount of study treatment and will be based on the actual treatment received.

13.1.2 Pharmacokinetic Population

The PK population will comprise all subjects who received any amount of NS101 and have sufficient post-dose serum concentration-time data to determine at least one PK parameter.

13.1.3 Pharmacodynamic Population

The PD population will include all subjects having received at least one dose of NS101, as appropriate, and for whom at least one post-dose PD parameter (FAM19A5 in plasma or CSF) can be adequately characterized.

13.1.4 Immunogenicity Population

The Immunogenicity population will include all subjects who have received any amount of NS101 and have at least one post-dose ADA/NAb measurement.

13.2 Safety and Tolerability Parameters and Analyses

Demographic parameters will be summarized descriptively.

Safety and tolerability to NS101 will be evaluated through the assessment of AEs (i.e., seriousness, severity, relationship to the study drug, outcome, duration, and management), vital signs, 12-lead ECG, clinical laboratory parameters, weight, and physical examination. TEAEs will be tabulated by study treatment. Changes from baseline values in vital signs, ECG, and clinical laboratory parameters tabulated by study treatment will be evaluated.

Safety and tolerability data will be reported using descriptive statistics. No inferential statistical analysis of safety data is planned. A complete description of the statistical analyses to be performed on the safety and tolerability data will be presented in the SAP.

13.3 Pharmacokinetics

13.3.1 Pharmacokinetics from Serum Samples

The following PK parameters will be calculated by standard non-compartmental methods for serum NS101:

- 1) AUC₀₋₂₄: area under the concentration-time curve from time zero to time 24 hours
- 2) AUC_{0-t}: Area under the concentration-time curve from time zero until the last observed concentration
- 3) AUC_{0-inf}: Area under the concentration-time curve from time zero to infinity (extrapolated)
- 4) Residual area: Percentage of AUC_{0-inf} due to extrapolation from the time of the last observed concentration to infinity, calculated as $[1 (AUC_{0-t}/AUC_{0-inf})] \times 100$
- 5) C_{max}: Maximal observed concentration
- 6) T_{max} : Time of C_{max}
- 7) $T_{\frac{1}{2}}$ el: Terminal elimination half-life
- 8) K_{el}: Elimination rate constant
- 9) CL: total body clearance calculated as Dose/AUC_{0-inf}
- 10) V_z: apparent volume of distribution, calculated as Dose / (K_{el} x AUC_{0-inf})

13.3.2 Pharmacokinetics from CSF Samples

A listing of all NS101 concentrations in CSF will be presented, as well as ratio of NS101 in serum to NS101 in CSF.

Additional PK analysis may be performed.

Upon Sponsor's request, PK repeats might be performed according to Syneos Health's SOP. If reassays are requested for PK reasons, final results will include re-assay values, while results with original values will be presented in an appendix of the clinical study report as supportive data.

13.4 Pharmacodynamics

13.4.1 Pharmacodynamics from Plasma Samples

PD will be evaluated through the variation of level of FAM19A5 following administration of NS101. Baseline is defined as the Day 1 pre-dose PD sample. Changes in baseline FAM19A5 levels (Δ FAM19A5) will be determined. At each post-dose measurement of FAM19A5, the Day 1 pre-dose PD sample will be subtracted to calculate Δ FAM19A5.

The following PD parameters will be calculated for plasma FAM19A5:

- 1) AUEC_{0-t}: area under the PD effect versus time curve from time zero until the last measurable timepoint
- 2) E_{max}: maximal observed effect
- 3) TE_{max} : time of E_{max}

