	• Effect (E): variation of level of FAM19A5 (Δ FAM19A5) following administration of NS101:
	o PD: Change in baseline of FAM19A5 levels
	o PD parameters in plasma: AUEC _{0-t} , E _{max} , TE _{max} .
	o Concentrations of FAM19A5 in CSF.

Study Design:	This will be a single center, Phase 1, double-blind, randomized, placebo-controlled, sequential SAD study, consisting of 8 cohorts (Cohorts 1 to 8).
Subjects:	Up to 80 healthy adult males, \geq 18 and \leq 55 years of age, are planned to be enrolled in the study.
	The study will consist of 6 cohorts (Cohorts 1 to 8, 1 cohort per dose level). Each cohort will include 8 subjects (6 subjects receiving a single dose of the study drug NS101 and 2 subjects receiving a single dose of a matching placebo), for a total of 64 subjects planned for evaluation. All cohorts will receive the study drug under fasting conditions.
	For all cohorts, a staggered dosing schedule will be used and will include 2 sentinel subjects (1 active and 1 placebo) dosed initially (a minimum of 1 hour apart between end of infusion of first sentinel and start of infusion for second sentinel), and the remaining subjects dosed no sooner than 48 hours after the start of sentinel dosing.
	Cohorts will be dosed sequentially in an ascending design, with at least 14 days between sentinel dosing of each dose level. When safety/tolerability results from the Day 8 visit for the last subject in a cohort (e.g., Cohort 1), as well as available PK data up to 48 hours post-start of infusion, are available, safety parameters will be evaluated by a Safety Review Committee (SRC) to determine the overall safety of that dose level before proceeding to the next dose level.
	The SRC (composed of at least the Investigator, one medically qualified Sponsor representative and an independent medical monitor) will review the safety, tolerability, and available PK data in order to make decisions regarding continuation of the study at the next prescribed dose level, decreasing the next dose level, repeating a dose level, or not evaluating any additional dose level, based on consideration of the clinical significance of several safety and tolerability parameters.
	The SRC meeting will be held after at least 7 subjects from the same cohort have been dosed and followed up until the safety and tolerability data have been collected up to 7±1 days post-infusion for non-sentinels (approximately 9±1 days for sentinels) are available.

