8.3 Starting Dose

The calculation of the starting dose for the SAD part of this FIH study was done based on the methodology described in the FDA Guidance Estimating the Maximum Safe Starting Dose in Initial Clinical Trials for Therapeutics in Adult Healthy Volunteers² and considering the recommendations laid down in the EMA Guideline on strategies to identify and mitigate risks for first-in-human and early clinical trials with investigational medicinal products.³

The starting dose was selected based on the totality of the available data from the nonclinical pharmacology, PK and toxicology studies. For determination of the maximum recommended starting dose (MRSD), the following data was considered:

- The NOAEL observed in both rats and Cynomolgus monkeys was 300 mg/kg. However, the important presence of ADAs in Cynomolgus monkeys, in particular, NAbs, does not permit to draw any clear conclusions, since exposure to NS101 may be underestimated. Therefore, PK results from Cynomolgus monkeys were not used for the current FIH study, and their toxicology data was not used to determine the doses or other design elements.
- Rather, the NOAEL value of 300 mg/kg from rats was converted into Human Equivalent Doses (HEDs) by division using a conversion factor of 6.2, and assuming that doses scale 1:1 between animal models and humans, when normalized to body surface area. The HED obtained was 48.4 mg/kg. A potential starting dose of 4.84 mg/kg would provide a dose-based safety margin of 10-fold.
- Additionally, after IV administration of NS101 in a PK-PD study (section 5.2.1.2) at doses ranging from 0.1 to 30 mg/kg in mice, an increase in levels of FAM19A5 appeared at the 0.3 mg/kg dose, which was then identified as the minimally pharmacologically active dose. Mice treated with 10 mg/kg NS101 showed higher FAM19A5 levels 3 days after treatment than 1 day after treatment. FAM19A5 levels 3 days post-treatment with NS101 were similar between the dose of 10 and 30 mg/kg NS101. A dose of 3 mg/kg was the nearest tested dose below the 10 mg/kg dose. Contrary to the higher tested doses, its pharmacological effect decreased on Day 3. Based on these data, a safe pharmacologically active dose (PAD) in mice was established at 3 mg/kg and the HED derived from this PAD is 0.244 mg/kg (rounded up to 0.25 mg/kg). Therefore, a starting dose of 0.25 mg/kg is anticipated to elicit a very low degree of pharmacological activity.

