11.8.2 Blood Sampling for PD Analysis

A total of 14 blood samples will be collected in each cohort for PD analysis: pre-dose and 1, 4, 6, 12, 24 (Day 2), 36 (Day 2), 48 (Day 3), 96 (Day 5±1), 168 (Day 8±1), 336 (Day 15±1), 504 (Day 22±2), 672 (Day 29±2), and 1416 (Day 60±3) hours post-start of infusion (3 mL for each sampling time).

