9.2 Plasma PD Sampling Schedule

A total of 14 blood samples will be collected in each cohort for PD analysis: pre-dose (baseline) and 1, 4, 6, 12, 24, 36, 48, 96, 168, 336, 504, 672, and 1416 hours post-start of infusion.

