9.3 Plasma PD Parameters

Individual and mean plasma concentration versus time curves will be presented for both linear and semi-log scales for normalized and actual FAM19A5.

Normalized and actual plasma FAM19A5 and changes from baseline Δ FAM19A5, along with PD parameters will be presented in data listings and summarized in tables by treatment, using descriptive statistics (n, arithmetic mean, geometric mean, SD, CV%, min, max, and median).

The following PD parameters will be calculated for plasma normalized and actual FAM19A5:

Parameter	Definition
AUEC _{0-t}	area under the PD effect versus time curve from time zero until the last measurable timepoint
E _{max}	maximum observed effect
TE _{max}	time of E _{max}

AUEC_{0-t}, will be calculated using the linear trapezoidal method (linear up log down).

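### Plasma Emax is the largest of 13 changes from one pre-dose sample, so low-effect doses show a positive mean Emax by chance, and the plan does not assure the placebo figures that would reveal this

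*Protocol*

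**What the plan says.** Protocol 13.4.1 fixes the reference value: "Baseline is defined as the Day 1 pre-dose PD sample". At every later measurement "the Day 1 pre-dose PD sample will be subtracted". SAP section 9 repeats the rule for both actual and normalised FAM19A5. Protocol section 7 defines the effect as the "variation of level of FAM19A5" after dosing, so the plasma parameters are taken on the change. Emax is its maximum, TEmax the time of that maximum, and AUEC0-t the "area under the PD effect versus time curve from time zero until the last measurable timepoint" (SAP 9.3), by a linear-up, log-down rule.

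Protocol 11.8.2 states: "A total of 14 blood samples will be collected in each cohort for PD analysis". SAP 9.2 gives the times: "pre-dose (baseline) and 1, 4, 6, 12, 24, 36, 48, 96, 168, 336, 504, 672, and 1416 hours post-start of infusion".

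On placebo the text points two ways. Protocol 13.1.3 and SAP 5.6 limit the PD population to men who received NS101, qualified only by the words as appropriate, and SAP section 9 uses that population for all plasma PD summaries. Yet SAP 9.3 tabulates the PD parameters by treatment, and SAP 6.1 puts an All Placebo group first among the labels for by-treatment tables. Neither document specifies a placebo-corrected Emax or AUEC.

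**The concern.** The maximum of many noisy differences lies above zero on average even when nothing has happened, and enrolling more men does not average this away. It matters where true activity is small. Protocol 8.3 says that "a starting dose of 0.25 mg/kg is anticipated to elicit a very low degree of pharmacological activity", and Protocol 5.4.2 expects little or no activity at the lower dose levels. There, a positive mean Emax could be read as target engagement. AUEC has a different weakness: any error in the single baseline sample enters every change and is carried over the whole follow-up.

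SAP section 3 gives dose selection for later studies as a purpose of the trial, and Emax, TEmax and AUEC0-t are its only derived plasma PD parameters. Without placebo values computed the same way, a reader cannot tell the no-effect level from a small effect.

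**Working it through.** **Inputs.** The sampling times are from SAP 9.2, the single baseline from Protocol 13.4.1, and 6 active and 2 placebo men in each of 8 cohorts from SAP 3.3. The documents give no SD or CV for human FAM19A5. I keep the within-man SD as σ and, as an assumption, show a CV of 10-30%. Emax is taken as the largest increase. The plan does not state its direction; if the largest absolute change were meant, it could never be negative.

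**1. The plan's figures.** The list has 14 times, 13 of them post-dose. Day 60 is 59 × 24 = 1416 h. Both agree with the documents.

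**2. Emax with no effect.**
- Emax = max(X1,…,X13) − X0. With independent normal errors, simulation of 400,000 men gives a mean of +1.67σ and an SD of 1.15σ.
- Emax exceeds zero unless the baseline is the highest of 14 exchangeable values, so P(Emax > 0) = 13/14 = 92.9%.
- A six-man mean is positive in more than 99.9% of cohorts (95% range 0.76σ to 2.59σ).
- As a share of baseline: 1.67 × 10% = +17%, and 1.67 × 30% = +50%.
- Each of the 13 times is equally likely to hold the maximum, so the median TEmax is the seventh time, 48 h. Protocol 5.2.1.2 reports a peak at 36-48 h in rats given 10 mg/kg, so a chance TEmax could look like the expected one.
- With serially correlated errors (time constants of 24-168 h) the mean is 1.38 to 1.60 SD. If half of the variance is a lasting offset, it is 1.18 of the total SD. That offset cancels in the change, and 1.18/√0.5 is again 1.67 of the SD that remains.

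**3. AUEC0-1416 with no effect (linear trapezoid).**
- The post-dose weights sum to 1415.5 h, which is the multiplier on the baseline error. Their sum of squares is 422,063.
- SD per man = σ√(1415.5² + 422,063) = 1557σ·h.
- Baseline share of variance = 1415.5²/(1415.5² + 422,063) = 82.6%. The mean error is zero.
- Expressed as a doubling of FAM19A5: 1557 × 0.10/24 = 6.5 days and 1557 × 0.30/24 = 19.5 days per man. For a six-man mean, divide by √6: about 2.6 to 7.9 days.
- The log-down rule cannot be applied to a change at or below zero, and SAP 9.3 does not say what happens then. With no effect, 13/14 of men have at least one negative change.

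**4. With a true effect.**

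| True time-averaged change (σ) | 0.5 | 1 | 2 | 3 | 5 |
|---|---|---|---|---|---|
| Baseline error, share of mean squared AUEC | 68% | 45% | 19% | 10% | 4% |

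| True peak (σ; assumed profile peaking at 36 h) | 1 | 2 | 5 | 10 |
|---|---|---|---|---|
| Bias of Emax (σ) | 1.06 | 0.67 | 0.20 | 0.03 |

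At a CV of 10-30% a doubling is 10σ down to 3.3σ, so a multi-fold rise lies towards the right of the second table.

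**5. Possible remedies.**
- *Dose mean Emax minus pooled placebo mean Emax.* With no effect the two have the same expectation, so the bias is 0. The standard error is 1.15σ × √(1/6 + 1/16) = 0.55σ.
- *Peak of the placebo-corrected mean curve.* This is still a maximum over 13 times: 1.67σ × √(1/6 + 1/16) = +0.80σ with no effect.
- *AUEC0-672.* The SD is 731σ·h and the baseline share 84%. Noise per hour of window is 1.09σ, against 1.10σ for 0-1416 h.
- *Averaging two or three pre-dose samples.* The AUEC SD falls from 1557 to 1193 or 1044σ·h, but mean Emax stays near 1.67σ.

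**The case against.** The strongest reply is that little depends on these parameters. The PD endpoints are exploratory and descriptive, escalation rests on safety and PK (Protocol 9.1), and no decision rule uses Emax or AUEC. SAP section 9 also summarises levels, absolute changes and percent changes at each time, and SAP 9.3 adds mean curves, so the course of the mean is visible without Emax. A placebo column may already be intended under SAP 6.1 and 9.3. All of this stands and limits the consequence. It does not settle the population wording, and the per-time summaries do not correct the named parameters.

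A second reply is that no dose is shown to be inactive. The 0.25 mg/kg dose was scaled from 3 mg/kg in mice, ten times the 0.3 mg/kg called minimally active there (Protocol 8.3). That is fair. The point therefore concerns doses with little or no effect, without asserting which doses those are.

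A reader might infer that AUEC is mostly baseline noise throughout. The documents do not support that. They give no human SD or effect size, and their rat data show large rises in blood FAM19A5 (Protocol 5.2.1.2). In the calculation, baseline error dominates only where the time-averaged change is below about one within-man SD. Nor should the 6.5-19.5 days be applied to comparisons between doses, because it is a per-man figure.

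**Conclusion.** The point holds for doses with little or no effect. There, mean Emax is positive by chance: +1.67 within-man SD with independent errors, about 1.2 to 1.6 SD with serial correlation, or +17% to +50% of baseline at an assumed CV of 10-30% with independent errors. TEmax is then close to a random sampling time. This concerns means; about 7% of unaffected men would still have an Emax at or below zero. AUEC0-t is unbiased but noisy, with about 83% of its no-effect variance from one sample and a noise SD for a six-man mean worth about 2.6 to 7.9 days of doubled FAM19A5 (same CV range, independent errors, linear trapezoid). At doses with a multi-fold rise both problems are small.

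The gap in the plan is that the placebo reference is implied in one place and excluded in another. It is worth correcting because the correction is cheap. It does not threaten the trial's primary conclusions.

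**What to change.** - **Protocol 13.1.3 and SAP 5.6:** include placebo men with post-dose FAM19A5 data in the PD population.
- **SAP 9.3:** tabulate Emax, TEmax and AUEC0-t for pooled placebo (2 × 8 = 16 men if all contribute), computed exactly as for active men. Report each dose's difference from pooled placebo in mean Emax and mean AUEC0-t, with a descriptive 90% CI. State the direction of Emax and the AUEC rule for changes at or below zero.
- **SAP section 9:** add the placebo-corrected mean change at each nominal time.

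Do not replace Emax with the peak of the placebo-corrected mean curve and a plain CI, since that peak is again selected from 13 times. A shorter AUEC window should not be presented as a cure for baseline noise.

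The cost is SAP and population wording and a few table rows; Protocol 11.3 already has placebo samples analysed. There are two downsides. Pooled placebo men come from different cohorts. And at active doses the Emax difference understates the peak: with a true peak of 10 SD it is off by 0.03 − 1.67 = −1.64 SD. Unadjusted Emax should therefore stay in the table beside it.
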